9. ELIGIBILITY CRITERIA: INCLUSION

Pre-SCT

1. Adult (≥ 18 y) patients undergoing their first T cell replete allo-HCT for chronic lymphocytic leukemia (CLL), Hodgkin Lymphoma (HL), or the following subtypes of Non-Hodgkin lymphoma: Mantle cell lymphoma (MCL) and follicular center cell lymphoma (FL)
2. Meeting institutional criteria for allo-HCT. Ejection fraction by echocardiogram or MUGA $>40\%$, pulmonary function test with adjusted DLCO $\geq 60\%$
3. Matched (8/8) or mismatched (7/8) related, unrelated HCT
4. Stem cell source: bone marrow, peripheral blood stem cell
5. Disease criteria:

Cohort A:

CLL

- Disease burden: lymph node size <5cm and/or extra-nodal involvement <5 cm

AND

- 17 p deletion (detected by any assay) ($\geq 20\%$ of cells involved if assay is conventional cytogenetics or FISH) or NOTCH mutation at any time point during disease course. Patient should have received at least 1 line of therapy. Prior ibrutinib therapy is permitted.

OR

- Relapsed/refractory CLL ≥ 2 lines of therapy. Prior ibrutinib therapy is permitted

MCL

- Disease burden: lymph node size <5 cm and/or extra-nodal involvement < 5 cm
- Relapsed/refractory MCL ≥ 1 line of therapy. Prior ibrutinib therapy is permitted. Prior autologous HCT is permitted.
- MCL blastoid variant in CR1 or high risk MCL being considered for allo HCT in CR1

Cohort B:

FL

- Disease burden: lymph node size <5cm and/or extra-nodal involvement <5 cm

AND

- Relapsed/refractory FL ≥ 2 lines of therapy. Prior ibrutinib therapy is permitted.

HD

- Disease burden: lymph node size <5cm and/or extra-nodal involvement <5 cm

AND

- Relapsed/refractory HD ≥ 2 lines of therapy

6. Preparative regimen: both reduced intensity and ablative regimens are permitted. Each center will pre-specify the regimen they intend to use during the conduct of the study
7. Donor criteria: HLA $\geq 7/8$ related or unrelated donors.
8. Women of childbearing potential and men who are sexually active must be practicing a highly effective method of birth control during and after the study consistent with local regulations regarding the use of birth control methods for subjects participating in clinical trials. Men must

agree to not donate sperm during and after the study. For females, these restrictions apply for 1 month after the last dose of study drug. For males, these restrictions apply for 3 months after the last dose of study drug.

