10. ELIGIBILITY CRITERIA: EXCLUSION

Pre-SCT

1. Progression of CLL or MCL or FL or HD at time of transplant
2. Use of Coumadin (warfarin) or other vitamin-K antagonists for anticoagulation. Non-coumadin anticoagulation is permitted.
3. Known CNS involvement
4. Active uncontrolled bacterial or invasive fungal infections
5. History of malignancy other than the underlying disease unless treated with a curative intent and/or no evidence of disease for at least 3 y OR expected to be cured with SCT
6. Planned use of post-HCT cyclophosphamide for GVHD prophylaxis
7. Anticipated planned donor lymphocyte infusion in the first 3 months post-SCT
8. T deplete HCT
9. Umbilical cord HCT
10. History of stroke or intracranial hemorrhage within 6 months of enrollment.

11. Clinically significant cardiovascular disease such as uncontrolled or symptomatic arrhythmias, congestive heart failure, or myocardial infarction within 6 months of Screening, or any Class 3 (moderate) or Class 4 (severe) cardiac disease as defined by the New York Heart Association Functional Classification.
12. Known HIV
13. Active Hepatitis B or C virus
14. Child-Pugh Class C

Prior to Administration of Ibrutinib (Day 60-Day 90 Post SCT)

1. In the critical care unit, or use of mechanical ventilation or use of renal replacement therapy at any time post HCT and prior to administration of ibrutinib
2. Active uncontrolled stage 3-4 acute GI GVHD prior to administration of ibrutinib
3. Active uncontrolled stage 4 acute liver GVHD prior to administration of ibrutinib
4. Evidence of progressive disease as compared to pre-HCT (persistence of disease is permitted)
5. Anticipated planned donor lymphocyte infusion in the first 3 months post-SCT
6. Active uncontrolled bacterial or invasive fungal infections
7. Prednisone equivalent of >2mg/kg for treatment of GVHD prior to administration of ibrutinib
8. Use of second line systemic therapy for treatment of acute GVHD prior to administration of ibrutinib
9. Any life-threatening illness, medical condition, or organ system dysfunction which, in the investigator's opinion, could compromise the subject's safety, interfere with the absorption or metabolism of ibrutinib capsules, or put the study outcomes at undue risk including the presence of chronic/active HBV and HBC infections and Child-Pugh Class C.
10. Major surgery or a wound that has not fully healed within 4 weeks of starting ibrutinib

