Persistent bone marrow nodules on bone marrow biopsy in patients achieving a CR or PR. Lymphoid aggregates should be evaluated with immunohistochemistry to determine whether they are comprised of CLL cells, lymphocytes other than CLL cells, or T cells.

18.3.5 Stable Disease:

Patients, who do not meet the criteria for a complete remission, partial remission, or progressive disease, have stable disease. Stable disease is therapeutically equivalent to a nonresponse (i.e., refractory disease).

18.4 The Following Established Definitions of Relapse, Recurrence and Responses Will Be Used for MCL and FL

18.4.1 Progressive disease or relapse is defined if one of the criteria is documented (either PET/CT or CT can be used).

PET-Based Response:

- Progressive metabolic disease
- Score of 4 or 5 (on a 5-point scale) with an increase in intensity of uptake from baseline and /or
- New FDG-avid foci consistent with lymphoma rather than another etiology (infection, inflammation). If uncertain regarding etiology of new lesions, biopsy or interval scan may be considered.

CT-Based Response:

- An individual node/lesion must be abnormal with an LDi > 1.5 cm and Increase by $\geq 50\%$ from PPD nadir and an increase in LDi or SDi from nadir (0.5 cm for lesions ≤ 2 cm, 1.0 cm for lesions > 2 cm)
 - In the setting of splenomegaly, the splenic length must increase by > 50% of the extent of its prior increase beyond baseline (for e.g., a 16-cm spleen must increase to > 17.5 cm). If no prior splenomegaly, must increase by at least 2 cm from baseline[¥]
 - New or recurrent splenomegaly
 - New or clear progression of preexisting non-measured lesions
 - A new node >1.5 cm in any axis
 - A new extranodal site >1.0 cm in any axis; if <1.0 cm in any axis its presence must be unequivocal and must be attributed to lymphoma.
 - Assessable disease of any size unequivocally attributable to lymphoma
 - New or recurrent Bone marrow involvement
- ¥ Spleen size baseline 13 cm in vertical length

LDi: longest transverse diameter of a lesion; SDi: Shortest axis perpendicular to LDi; PPD: cross product of LDi and SDi.

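### The MCL progression list in 18.4.1 includes lymphoma of any size without requiring it to be new or recurrent, so read literally persistent residual disease is a primary PFS event

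*Combined protocol and SAP*

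**What the plan says.** Section 18.4.1 governs MCL and FL: "Progressive disease or relapse is defined if one of the criteria is documented (either PET/CT or CT can be used"). Each bullet is therefore sufficient alone.

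Most bullets in the CT-based list are tied to change. The measured-node and spleen bullets require an increase from nadir or baseline, and the non-measured-lesion bullet requires new lesions or clear progression. The lesion bullets next to the one at issue read "A new node >1.5 cm in any axis", "A new extranodal site >1.0 cm in any axis" and "New or recurrent Bone marrow involvement". Between the last two stands "Assessable disease of any size unequivocally attributable to lymphoma", which has no such qualifier. No heading or footnote supplies one. The same bullet appears for HD in 18.5.

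Elsewhere the protocol expects residual lymphoma:

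- The MCL inclusion criteria in section 9 admit patients with nodal or extranodal disease below 5 cm.
- Section 10, item 4 of the pre-ibrutinib exclusions, reads "Evidence of progressive disease as compared to pre-HCT (persistence of disease is permitted"). The synopsis says the same.
- Section 18.4.3 defines PET-based partial remission so as to allow a residual mass of any size, and CT-based partial remission as a 50% decrease.
- CT-based stable disease applies only if no progression criterion is met.

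Section 24.1 counts progression or relapse as a PFS event from the date of transplant and restricts the primary analysis to cohort A (CLL and MCL).

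**The concern.** The primary endpoint depends on what counts as progression. As printed, a patient transplanted with residual MCL whose disease is unchanged or shrinking at the day 30 to 60 reassessment meets a progression criterion, provided the disease is clearly lymphoma. The same scan can also meet the partial-remission definition. The stable-disease category does not resolve the conflict, because it defers to the progression list.

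Two readers could therefore score one scan differently: an event within two months of transplant, or no event at all. The trial has a single arm and is compared with a fixed historical rate, so no concurrent control group would absorb a difference in scoring.

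**Working it through.** **1. The texts side by side, for a patient with persistent, unequivocal MCL on CT**

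| Text | Literal result |
|---|---|
| 18.4.1, the unqualified bullet plus the one-criterion rule | Progression |
| 18.4.1, growth and new-lesion bullets | Not progression |
| 18.4.3, partial remission (if the disease has shrunk enough) | Partial remission |
| 18.4.3, CT-based stable disease | Unavailable, because a progression criterion is met |
| Section 10, pre-ibrutinib item 4 | Persistence permitted |
| 24.1, PFS | Event if scored as progression |

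These cannot all hold. Within the primary analysis the conflict is confined to MCL. CLL uses 18.3.1, which has no such bullet, and FL and HD are in cohort B.

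**2. Reproducing the plan's power**

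Inputs from 24.1 and 24.2: N = 65; two-sided level 0.05; 2 years of uniform accrual and 2 years of follow-up; historical 1-year PFS 0.62 (CLL) and 0.52 (MCL); 25% relative improvement.

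Method: exponential PFS with mean θ = −1/ln(1-year PFS); φ = θ^(−1/3); Q = 65 × E[1 − exp(−L/θ)] with L uniform on 2 to 4 years; standard error = φ/(3√Q); power = Φ[(φ0 − φ1)/SE1 − 1.96].

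At a 50/50 mix:

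- Historical rate: 0.5 × 0.62 + 0.5 × 0.52 = 0.57, so θ0 = 1.779 and φ0 = 0.8253.
- Target: 0.57 × 1.25 = 0.7125, so θ1 = 2.950, φ1 = 0.6973, Q = 41.0 and SE = 0.0363.
- Power: Φ[(0.8253 − 0.6973)/0.0363 − 1.96] = Φ(1.57) = 94%. The plan states 93%.

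All 15 cells of the plan's table reproduce within 2 points.

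**3. Illustration of literal scoring**

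Let f be the share of MCL patients, otherwise progression-free at 12 months, who have residual assessable lymphoma. The documents do not give f, so it is an assumption and a range is shown. Apply the planned 25% gain to each disease: CLL 0.62 × 1.25 = 0.775; MCL 0.52 × 1.25 = 0.65. With CLL share w, the observed rate is w × 0.775 + (1 − w) × 0.65 × (1 − f).

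| CLL/MCL | f | 12-month PFS | Power |
|---|---|---|---|
| 50/50 | 0 | 0.713 | 94% |
| 50/50 | 5% | 0.696 | 87% |
| 50/50 | 10% | 0.680 | 76% |
| 50/50 | 20% | 0.648 | 45% |
| 30/70 | 10% | 0.642 | 58% |
| 70/30 | 10% | 0.718 | 89% |

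For the 30/70 and 70/30 mixes, power at f = 0 is 91% and 96%.

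In patients at 50/50: 65 × 0.5 × 0.65 = 21.1 MCL patients would be progression-free at 12 months. Five to 20% of these is 21.1 × 0.05 = 1.1 to 21.1 × 0.20 = 4.2 patients.

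The calculation assumes that every affected patient is scored literally and keeps the plan's exponential model. Literal events would cluster at the first scan, so the power figures are approximate.

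**The case against.** The best reply is that the intended meaning can be recovered. The bullet sits among new-lesion bullets. If lymphoma of any size were progression, the growth thresholds in the same list and the CT-based partial-remission category would have almost nothing left to do. This is persuasive about intent, and it is why the point is a wording defect and not a finding that the trial will score residual disease as failure.

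Second, section 18.1 has a review committee read all response assessments. That makes uniform, uncorrected literal scoring less likely. It does not settle the matter, because the committee has no written instruction to disregard unchanged residual disease.

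Third, exposure is limited. The disease must be unequivocally lymphoma, so a residual mass alone does not qualify. PET/CT may be used instead of CT, and the PET route requires increased uptake or new foci. MCL patients may also be enrolled in first complete remission. All of this stands and argues for small values of f.

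A reader might also infer that patients with persistent disease would be refused ibrutinib as having progressed. The documents do not support that. The pre-ibrutinib exclusion sets its own comparison with the pre-HCT state and expressly permits persistence, and the coordinating center approves a second checklist before treatment starts.

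Nor do the documents support the inference that the planned gain would vanish. At a 30/70 mix with f = 30% the observed rate is 0.551 against a historical 0.55, but that needs a high MCL share, a high share with residual disease and literal scoring of every case. None of the three can be established from the documents.

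**Conclusion.** The defect is real. A sufficient criterion in the primary event definition lacks the qualifier that its neighbours carry and, followed as written, contradicts the partial-remission definition and the permission for persistent disease. New disease was probably meant, but no rule says so.

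The size is unknown. Under uniform literal scoring at a 50/50 mix with f between 5% and 20%, 12-month PFS falls by about 2 to 6.5 points (0.325 × f), and power falls from about 94% to between 87% and 45%. Only one to four patients are involved, so occasional literal scoring would matter.

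The error runs against ibrutinib only if the historical 52% for MCL did not count persistent disease as progression. The plan does not give the rule behind that figure, so the direction is conditional too. The repeat of the bullet for HD has no bearing on the primary PFS.

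**What to change.** In 18.4.1 and 18.5, begin the bullet with the words *new or recurrent*. Adding *new* alone could drop a small recurrence at a site that had resolved, although the list is meant to cover relapse as well as progression.

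Add one sentence to the same sections: disease present before HCT that persists without meeting the growth criteria is not a progression event. Refer to that sentence in the PFS definition in 24.1 and give it to the review committee as its written rule, so that section 18, the pre-ibrutinib criteria in section 10 and the primary analysis agree.

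The cost is a few words in two lists, one sentence and a cross-reference, by protocol amendment. No new assessments are needed. If response assessments have already been adjudicated, MCL cases scored as progression on this bullet alone should be re-read under the clarified rule, with the number reported.

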18.4.2 Complete remission is defined by the following criteria (should meet all criteria)

PET-Based Response:

- Complete metabolic response with a score of 1, 2 or 3 with or without residual mass on a 5-point scale

CT-Based Response:

- Target nodes/nodal masses must regress to ≤ 1.5 cm in LDi
- No extralymphatic sites of disease
- Absence of non-measured lesions
- No new lesions
- Bone marrow normal by morphology and if indeterminate, IHC negative

18.4.3 Partial Remission is defined by the following criteria:

PET-Based Response

- Score 4 or 5 with reduced uptake compared with baseline and residual mass(es) of any size

CT-Based Response

- 50% decrease in SPD of up to six target measurable nodes and extranodal sites [£]
 - £ When a lesion is too small to measure on scan, 0.5x0.5 cm is the default value, if no longer visible 0x0 cm, for a node greater than 0.5 x0.5 cm but smaller than normal use the actual measurement for calculation.
- Spleen must have regressed by >50% in length beyond normal

Stable disease:

PET-based response

- No metabolic response with a score of 4 or 5 on the five point scale

CT-based response

- >50% decrease from baseline in SPD of up to 6 dominant, measurable nodes and extranodal sites; no criteria for progressive disease are met

18.5 The following established definitions of relapse, recurrence and responses will be used for HD

Progressive disease or relapse is defined if one of the criteria is documented (either PET/CT or CT can be used)

PET-Based response:

- Progressive metabolic disease

- Score of 4 or 5 (on a 5-point scale) with an increase in intensity of uptake from baseline and /or
- New FDG-avid foci consistent with lymphoma rather than another etiology (infection, inflammation). If uncertain regarding etiology of new lesions, biopsy or interval scan may be considered.

CT based response:

- An individual node/lesion must be abnormal with an LDi > 1.5 cm and Increase by $\geq 50\%$ from PPD nadir and an increase in LDi or SDi from nadir (0.5 cm for lesions ≤ 2 cm, 1.0 cm for lesions > 2 cm)
- In the setting of splenomegaly, the splenic length must increase by > 50% of the extent of its prior increase beyond baseline (for e.g., a 16-cm spleen must increase to > 17.5 cm). If no prior splenomegaly, must increase by at least 2 cm from baseline[¥]
- New or recurrent splenomegaly
- New or clear progression of preexisting non-measured lesions
- A new node >1.5 cm in any axis
- A new extranodal site >1.0 cm in any axis; if <1.0 cm in any axis its presence must be unequivocal and must be attributed to lymphoma
- Assessable disease of any size unequivocally attributable to lymphoma
- New or recurrent Bone marrow involvement

¥ Spleen size baseline 13 cm in vertical length

LDi: longest transverse diameter of a lesion; SDi: Shortest axis perpendicular to LDi; PPD: cross product of LDi and SDi.

Complete remission is defined by the following criteria (should meet all criteria)

PET-based response:

- Complete metabolic response with a score of 1, 2, or 3 with or without residual mass on a 5-point scale

CT- based response:

- Target nodes/nodal masses must regress to ≤ 1.5 cm in LDi
- No extralymphatic sites of disease

- Absence of non-measured lesions
- No new lesions
- Bone marrow normal by morphology and if indeterminate, IHC negative

Partial Remission is defined by the following criteria:

PET-based response

- Score 4 or 5 with reduced uptake compared with baseline and residual mass(es) of any size

CT-based response

- >50% decrease in SPD of up to six target measurable nodes and extranodal sites [£]

[£] When a lesion is too small to measure on scan, 0.5x0.5 cm is the default value, if no longer visible 0x0 cm, for a node greater than 0.5 x0.5 cm but smaller than normal use the actual measurement for calculation.

- Spleen must have regressed by >50% in length beyond normal

Stable disease is defined by the following criteria:

PET-based response

- No metabolic response with a score of 4 or 5 on the five-point scale

CT-based response

- >50% decrease from baseline in SPD of up to 6 dominant, measurable nodes and extranodal sites; no criteria for progressive disease are met

Footnote: A score of 3 in many patients indicates a good prognosis with standard treatment, especially if at the time of an interim scan. However, in trials involving PET where de-escalation is investigated, it may be preferable to consider a score of 3 as inadequate response to avoid under treatment

19. REGISTRATION OF PATIENT

Each center will decide at time of study activation their preferred preparative regimens for HCT and complete the preparative regimen selection worksheet. Centers will not be allowed to deviate from their standard during the conduct of the study. Regimens will be stratified as reduced intensity (RIC), myeloablative (MAC) for related (matched and mismatched) and unrelated (matched and mismatched).

Prior to registration, a copy of the IRB approval at the site will be requested and kept on file at the

Vanderbilt-Ingram Cancer Center (VICC) Coordinating Center. Eligible participants will be entered on study centrally at the VICC Coordinating Center. All sites should email the Coordinating Center at [contact] to verify slot availability prior to enrollment.

All patients MUST be registered with the VICC prior to the start of the preparative regimen and again prior to start of protocol treatment. Registration can only be conducted during the business hours of 8AM – 5PM Central Standard Time Monday through Friday.

- 1) All sites must email the VICC CTSR Coordinating Center at [contact] to notify of upcoming registration and ensure slot availability. The following information should be included in your email:
 - Study number
 - Patient initials
 - Disease type
 - Anticipated consent date
 - Anticipated start date
- 2) If a subject ID number is required prior to patient enrollment (i.e. at screening due to sample collection requirement), the site must submit the following documents with their email notification to the Coordinating Center:
 - Copy of the patient's signed and dated Informed Consent including documentation of the consent process.
 - HIPAA authorization form (if separate from the main consent form)
 - VICC Patient Enrollment Form

The Coordinating Center will then provide a subject ID number via email.

- 3) Email the following documents to the Coordinating Center for eligibility review and patient enrollment ([contact]):
 - Copy of the patient's signed and dated Informed Consent, including documentation of the consent process.
 - HIPAA authorization form (if separate from the main consent form)
 - VICC Patient Enrollment Form
 - Eligibility supporting documents such as pathology reports, laboratory tests, etc. or EMR access. Note: all source documents should be de-identified and screening/subject ID number added prior to sending.
 - Tissue Block Registration Form (see the Lab Manual)
 - Signed and completed Eligibility Checklist. **To be eligible for registration to the study, the participant must meet each inclusion and exclusion criterion listed in the eligibility checklist.**

Note: All study documents should be received 24-48 hours prior to the patient's anticipated start date. Same day treatment registrations will only be accepted with prior notice and discussion with the Coordinating Center. Please email the Coordinating Center if enrollment is needed sooner.

Upon satisfactory review of eligibility documents submitted, the Coordinating Center will approve enrollment and issue a subject ID number if one was not issued at screening. Once registration/enrollment confirmation from Coordinating Center is received, proceed with protocol procedures.

Please contact the assigned Study Contact with any questions regarding this process. You can also reach out to your assigned CRA once the study is activated.

The VICC Coordinating Center will assign Subject ID numbers to all patients whose eligibility has been confirmed. Only patients deemed eligible will be registered to investigational treatment.

Sequence/study ID numbers will not be re-used if a patient screen fails. Following registration, eligible participants should begin study treatment consistent with the protocol no later than [XXX days/weeks] after registration/enrollment by the VICC Coordinating Center. If a participant does not receive protocol therapy following registration within the allowed time period, the participant's registration on the study will be canceled. The Study Contact should be notified of cancellations as soon as possible. Patients being re-screened will need to consent to repeated procedures. As such, the Coordinating Center will require a new, signed Informed Consent document.

Issues that would cause treatment delays should be discussed with the Protocol Chair. Any requests for eligibility exceptions and/or deviations must be approved in writing by the Protocol Chair and the VICC DSMC.

As is generally accepted, standard of care procedures performed prior to consent, but within the protocol defined screening window for each assessment, can be used for study purposes. All research-only procedures must be performed after patient consent.

